8.1 Efficacy Assessments and Procedures

Radiographic images and physical findings (physical assessments) will be used by the Investigators for the local determination of disease progression and participant treatment decisions. Refer to the RECIST 1.1 publication for additional information ([Eisenhauer 2009](#)).

Whenever available, the longest diameter measurement of each target lesion and short axis for nodes derived from historical computerized tomography (CT)/magnetic resonance imaging (MRI) scans over a period of up to 100 days prior to enrollment should be collected in order to assess tumor growth dynamics prior to study enrollment. For comparability, target lesions in both historical and on-treatment scans should match, if possible. Participants will have a chest and abdominal imaging scan (e.g., computed tomography, magnetic resonance imaging) as appropriate and, if clinically indicated, imaging scans of other body areas (e.g., bone, pelvis). Participants should have a repeat imaging scan as described in the Schedule of Activities in [Section 1.3](#). All imaging scans to assess disease progression should be performed using similar imaging platforms and imaging techniques, including the use or absence of contrast, and should be of consistent anatomic locations with prior imaging scans, whenever possible. At End of Study Intervention visit, the tumor assessment should only be performed if no disease progression was previously documented.

Imaging scans will be locally read for all parts of the study. The applicable overall response category for each visit that includes disease assessment, based on evaluation of imaging scan, will be recorded in the CRF. Determination of participant study disposition (i.e., discontinuation or extension of therapy) will be based on disease progression as interpreted from the local evaluation of the imaging scan.

For assessment time points and procedures for primary, secondary, and tertiary/exploratory efficacy endpoints, see Schedule of Activities ([Section 1.3](#)).

8.2 Safety Assessments and Procedures

The safety profile of the study intervention will be assessed through the recording, reporting and analysis of baseline medical conditions, adverse events (AEs), physical examination findings, vital signs, electrocardiograms, Eastern Cooperative Oncology Group performance status (see [Appendix 10](#)), and laboratory tests.

Comprehensive assessment of any potential toxicity experienced by each participant will be conducted starting when the participants give informed consent and throughout the study. The Investigator will report any AEs, whether observed by the Investigator or reported by the participant; the reporting period is specified in Section 8.3.1.

8.2.1 Physical Examinations

- A complete physical examination will include, at a minimum, assessments of the cardiovascular, respiratory, gastrointestinal and neurological systems.
- A brief physical examination will include, at a minimum, assessments of the skin, lungs, cardiovascular system, and abdomen (liver and spleen).
- Investigators will pay special attention to clinical signs related to previous serious illnesses.

8.2.2 Vital Signs

- Height at screening and weight will be measured and recorded as per timepoints noted in the Schedule of Assessments.
- Oral temperature, pulse rate, respiratory rate, and blood pressure will be assessed.
- Blood pressure and pulse measurements will be assessed in a supine position with a completely automated device. Manual techniques will be used only if an automated device is not available.
- Blood pressure and pulse measurements will be preceded by at least 5 minutes of rest for the participant in a quiet setting without distractions (e.g., television, cell phones).
- Vital signs will be measured in a semi-recumbent position after 5 minutes rest and will include temperature, systolic and diastolic blood pressure, and pulse.

8.2.3 Electrocardiograms

8.2.3.1 Standard Single 12-lead Electrocardiograms

Single 12-lead ECGs will be obtained as outlined in the Schedule of Activities using an ECG machine that automatically calculates the heart rate and measures PR, QRS, QT, and QTcF intervals.

8.2.3.2 Digital Triplicate Electrocardiograms

Triplicate 12-lead ECG will be obtained as outlined in the Schedule of Activities using an ECG machine that automatically calculates the heart rate and measures PR, QRS, QT, and QTcF intervals.

At each time point at which triplicate ECG are required outside of Holter collection, 3 individual ECG tracings will be obtained as closely as possible in succession, but no more than 2 minutes apart. The full set of triplicates will be completed in less than 4 minutes and will occur in a resting state without prior procedure such as blood draw.

8.2.4 Clinical Safety Laboratory Assessments

- Blood and urine samples will be collected for the clinical laboratory tests listed in [Appendix 6](#) at the time points listed in the Schedule of Activities. All samples will be clearly identified. See [Table 20](#).
- Additional tests may be performed at any time during the study, as determined necessary by the Investigator or required by local regulations.
- The tests will be performed by local laboratory.
- The Sponsor will receive a list of the local laboratory normal ranges before shipment of study intervention(s). Any changes to the ranges during the study will be forwarded to the Sponsor.
- The Investigator will review each laboratory report, document this review, and record any clinically relevant changes occurring during the study in the AE section of the CRF. The laboratory reports will be filed with the source documents.

Additional serum or highly sensitive urine pregnancy tests may be conducted, as determined necessary by the investigator or required by local regulation, to establish the absence of pregnancy at any time during the study.

8.3 Adverse Events and Serious Adverse Events

The definitions of an Adverse Event (AE) and a Serious Adverse Event (SAE) are in [Appendix 4](#).

The Investigator and any qualified designees (e.g., Sub-Investigators) are responsible for detecting, documenting, and recording events that meet the definition of an AE or SAE. The Investigator remains responsible for following up AEs that are serious or that caused the participant to discontinue the study intervention or study, as specified in [Section 8.3.3](#).

Requests for follow-up will usually be made via the Study Monitor, although in exceptional circumstances the global patient safety department may contact the Investigator directly to obtain further information or to discuss the event.

The method of recording, evaluating, and assessing causality of AEs and SAEs and the procedures for completing and transmitting SAE reports are in [Appendix 4](#).

8.3.1 Time Period and Frequency for Collecting Adverse Event and Serious Adverse Event Information

All SAEs will be collected from the signing of the ICF until the safety follow-up visit at the time points specified in the Schedule of Activities ([Section 1.3](#)). Beyond this reporting period, any new unsolicited SAEs that the Investigator spontaneously reports to the Sponsor will be collected and processed.

All AEs will be collected from the signing of the ICF until the safety follow-up visit at the time points specified in the Schedule of Activities.

AEs/SAEs that begin before the start of study intervention but after obtaining ICF will be recorded on the Medical History/Current Medical Conditions CRF, not on the AE CRF.

All SAEs will be recorded and reported to the Sponsor or designee immediately and under no circumstance will this exceed 24 hours, as indicated in [Appendix 4](#). The Investigator will submit any updated SAE data to the Sponsor within 24 hours of it being available using the same procedure that was used for the initial report.

Investigators are not obligated to actively solicit AEs or SAEs after the end of study participation. However, if the investigator learns of any SAE, including a death, at any time after a participant has been discharged from the study, and he/she considers the event to be reasonably related to the study intervention or study participation, the Investigator will promptly notify the Sponsor.

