4.1 Overall Design

This is an open-label, multicenter, Phase 1, clinical study of M4076 (see [Table 7](#)).

Part 1A is a M4076 monotherapy dose escalation designed to determine the safety, tolerability, PK, Pd and early signs of efficacy in participants with solid tumors. Once an RDE is declared in Part 1A, a preliminary food effect cohort, Part 1B, may follow and will be conducted at the RDE or a lower dose than RDE determined from Part 1A. Part 1B is a randomized, 2-sequence, 2-period, cross-over design.

Table 7 Summary of Overall Study Design

Study Part	Population	Design	Study Intervention
Part 1A	All patients with advanced solid tumors	Dose escalation enrolling patients in sequential cohorts at increasing dose levels.	M4076 monotherapy
Part 1B	All patients with advanced solid tumors	Once an RDE is determined in Part 1A, a preliminary food effect assessment will be included (2 x 2 randomized crossover).	M4076 monotherapy

RDE = recommended dose for expansion.

Individual participants will follow study procedures and assessments as shown in the Schedule of Assessment in Section 1.3. Section 1.2 presents the Study Schema for the study. For Part 1A, potential variations in study intervention schedules and schedule of activities due to alternative dosing schedules are found in [Appendix 7](#).

Duration of Study:

For each participant in Part 1A, the study will include a Screening period lasting up to 28 days. Participants will be treated until disease progression, death, or End of Study. It is estimated that participants will be on the study for an approximate duration of 105 days/15 weeks. There will also be an End of Study Intervention Visit (within 7 days after last dose), and a Safety Follow-up period of 30 days (± 7 days) after the last study intervention intake.

For each participant in Part 1B, the study will include a screening period lasting up to 21 days, a preliminary food effect assessment of 7 days followed by study intervention with M4076 monotherapy until disease progression or end of study. From Day 5 onward, participants will continue to be treated as for Part 1A with same visits.

Screening:

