Screening will be performed within 28 days prior to Day 1 of M4076 administration. If there are no clinically significant findings during Screening and the individual meets all the protocol-defined inclusion and none of the exclusion criteria, the individual will be considered eligible for participation in the study. Screening for the next cohort may be performed before the SMC has taken the decision on the next dose. The eligible participants screened for the next cohort will, however, only be treated after the decision for the next cohort has been taken by the SMC.

Individuals who fail to start study intervention, for instance due to unmet protocol-specified criteria or consent withdrawal, will be considered Screening Failures.

Study Intervention Period:

All participants will receive study intervention until disease progression (according to Response Evaluation Criteria in Solid Tumors Version 1.1, see [Appendix 9](#)), death, AE leading to discontinuation of study intervention(s), or withdrawal of consent, whichever occurs first.

Follow-up:

All participants are to be followed up after end of study intervention, including an End of Study Intervention Visit assessment (within 7 days of last dose). A Safety Follow-up Visit will occur 30 (± 7) days after the last dose of M4076 for all participants who discontinued the study intervention permanently.

See Section 4.3 for End of Study definition.

Assumptions and projections about the likely duration of the study intervention and efficacy phases are provided in Section 9.

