9.4.2 Safety Analyses

The DLT analysis will be performed on the DLT Analysis population. All other safety analyses will be performed on the Safety Analysis population. See [Table 17](#).

Table 17 Safety Analyses

Endpoint	Statistical Analysis Methods
Part 1A	
Primary	
DLT	
AEs classified as DLTs as assessed by SMC will be evaluated.
 
Bayesian dose toxicity analysis.
 
At primary analysis for Part 1A, the number and proportion of participants experiencing DLTs will be reported by dose level, based on observations during the first study intervention evaluation (21 days). Posterior probabilities (2.5%, 25%, 50%, 75%, and 97.5% quantiles) for DLT rates at selected doses will be estimated from the Bayesian dose toxicity model.
 
Sensitivity analysis using frequentist modeling (without prior).
 
Regarding intercurrent events: These are considered in the definition of DLTs and DLT analysis set.

Secondary	
AE	
AEs will be coded according to the latest available version of MedDRA. Severity of AEs will be graded using the NCI-CTCAE (Version 5.0). Missing classifications concerning study intervention relationships will be considered related to the study intervention. TEAEs are defined as AEs emerging or worsening after start of study intervention until 30 days after the end of study intervention period.
 
Following TEAEs will be presented in summaries by incidence and type according to MedDRA System Organ Classes and Preferred Terms:
 
 • TEAEs. • SAEs. • TEAEs related to study interventions. • NCI-CTCAE Grade 3 or higher TEAEs. • NCI-CTCAE Grade 3 or higher related TEAEs. • TEAEs leading to interruptions, dose modifications of study interventions. • TEAEs leading to permanent discontinuation of study interventions. • TEAEs leading to death.

Death	Counts and percentages.
Changes in laboratory measurements	Summary statistics and boxplots. Laboratory results will also be classified by Grade according to NCI-CTCAE. Worst on-treatment grades as well as shifts to worst on treatment grades will be summarized. Measurements without NCI-CTCAE grading will be summarized by above, within and below normal limits.

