## 9.6 Definition of On-treatment Period

The on-treatment period is defined as the time from the first dose of study intervention day to the last administration day of study intervention + 30 days, or the cut-off date or death, whichever occurs first.

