## 15.3 Deaths, Other Serious Adverse Events, and Other Significant Adverse Events

### 15.3.1 Deaths

All deaths, deaths within 30 days after last dose of study intervention, death within 60 days after first dose, as well as reason for death until end of study, will be tabulated based on information from the “Death” and “Survival Follow-Up” CRFs.

- Number of Deaths
- Number of Deaths within 30 days after last dose of M4076
- Number of Deaths within 60 days after first dose of M4076
- Primary Reason of Death
  - Progressive disease and/or disease related condition
  - Event unrelated to M4076
  - Event related to M4076
  - Unknown

In addition, a listing of Deaths will be provided, defined as any AE with Grade 5, or outcome “fatal” if grade 5 not applicable. This will be sorted by study part, dose level and participant. This listing will additionally contain age, sex, site of primary tumor, SOC, PT, verbatim, CTCAE grade, SAE (yes/no), DLT per investigator (yes/no), DLT per SMC, relatedness to M4076 (yes/no), start date (+treatment day), stop date (+treatment day), duration (in days), action taken with M4076, if treatment was stopped before start of AE: days since stop of treatment, outcome, as well as a flag for death within 30 days of last dose of study intervention and a flag for death within 60 days of first dose of study intervention.

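### Under Protocol 8.3.1, AE collection can stop 23 days after the last dose while TEAEs and 30-day deaths are counted to Day 30, and vital status for the 60-day death count has no scheduled contact behind it

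*Protocol*

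**What the plan says.** **When the visit happens.** Protocol 4.1 states: "A Safety Follow-up Visit will occur 30 (± 7) days after the last dose of M4076". The same section describes "a Safety Follow-up period of 30 days (± 7 days) after the last study intervention intake", and Table 1 gives the same window.

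**When collection stops.** Protocol 8.3.1 states: "All AEs will be collected from the signing of the ICF until the safety follow-up visit". SAEs stop at the same visit; later ones are processed only if the investigator reports them unprompted. Under 8.3.2, participants are asked about changes in their condition at study visits.

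**What the analysis counts.** Protocol 9.4.2 (Table 17) defines TEAEs as "AEs emerging or worsening after start of study intervention until 30 days after the end of study intervention period". SAP 9.6 ends the on-treatment period at "the last administration day of study intervention + 30 days", or at cut-off or death if earlier. SAP 15.3.1 tabulates "Number of Deaths within 30 days after last dose of M4076" and "Number of Deaths within 60 days after first dose of M4076", using the Death and Survival Follow-Up CRFs. SAP 9 bases proportions on the whole analysis set, and SAP 9.8 imputes nothing unless otherwise specified.

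**Text that points the other way.** The AE row of Table 1 extends assessment beyond the safety follow-up visit to the completion of the study. Protocol 4.4 says that participants who have not died, withdrawn consent or been lost should be followed until the last participant's safety follow-up visit, or until transfer to treatment access outside the study.

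**The concern.** The reporting window is fixed at 30 days after the last dose, but the collection window in 8.3.1 closes on a visit date that may come a week earlier. A new non-serious AE in the days between meets the TEAE definition and has no collection route under 8.3.1. An AE table counts records, so a day on which nobody asked looks the same as a day without an event. With the full analysis set as denominator, the incidence can only be understated.

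AE occurrence is one of the endpoints under the primary objective (Protocol Section 3), and safety beyond the DLT period feeds the choice of RDE (Protocol 4.1.1).

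The 60-day death count raises a related but separate question. It runs from the first dose, so someone who stops early can pass the last scheduled contact well before the window closes.

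**Working it through.** **Inputs.** Visit at 30 ± 7 days after last dose (Protocol 4.1, Table 1). TEAE, on-treatment and death windows of 30 days after last dose (Protocol 9.4.2, SAP 9.6 and 15.3.1). Death window of 60 days after first dose (SAP 15.3.1). DLT period of 21 days from first dose (Protocol 6.6.2).

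**1. The 30-day gap**
- Earliest visit: 30 − 7 = Day 23. Latest: 30 + 7 = Day 37.
- Gap = max(0, 30 − visit day), at most 30 − 23 = 7 days, and 7/30 = 23%.
- Of the 15 permitted visit days (23 to 37), 7 fall before Day 30. If visits were spread evenly (an assumption), the mean gap is (7+6+5+4+3+2+1)/15 = 28/15 = 1.9 days.

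**2. What the worst case could do to AE incidence.** Suppose that every visit is on Day 23, new AEs arise at a constant rate over the 30 days, and none after the visit is captured. If the true 30-day post-dose incidence is p, the recorded incidence is 1 − (1 − p)^(23/30). The values of p are assumptions, because the documents give none.

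| True p | Recorded |
|---|---|
| 10% | 7.8% |
| 30% | 23.9% |
| 50% | 41.2% |
| 70% | 60.3% |

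**3. Ceiling for 30-day deaths.** With constant hazard h = ln 2/(median in months × 30.4375), the probability of death between Day 23 and Day 30 is exp(−23h) − exp(−30h). For assumed median survival from last dose of 3, 6 and 12 months this is 0.043, 0.024 and 0.013. Among 28 participants (the top of the Part 1A range) that is 1.2, 0.7 and 0.4 deaths. These would be missed only if every visit were on Day 23 and no other source captured them.

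**4. The 60-day death window.** Let k be the days from first to last dose and v the visit day after last dose. Uncovered days = max(0, 60 − (k + v)).
- v = 23: uncovered when k < 37. v = 30: when k < 30. v = 37: when k < 23.
- For k = 20, the uncovered stretch is 17, 10 and 3 days for v = 23, 30 and 37.
- This gap therefore exists without the ± 7, and a one-sided visit window does not close it.

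**5. DLT analysis.** Even if the only dose is on Day 1, the earliest permitted visit is Day 1 + 23 = Day 24, after the 21-day DLT period has ended.

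**The case against.** The strongest reply is that 8.3.1 is not the only rule. The Table 1 note carries AE assessment on to study completion, and Section 4.4 asks for continued follow-up of most participants. The release from active solicitation in 8.3.1 applies after the end of study participation, which 4.4 may place later than the visit. Unprompted SAE reports are still processed, and known SAEs and AESIs are followed to resolution. This stands in part: a reader might infer that all safety collection ends at the visit, and the documents do not support that as a settled reading. But neither passage supplies a visit, contact or form after the safety follow-up visit. Later scans under the Table 1 imaging note are tumor assessments, not AE queries. What remains is a contradiction, with new non-serious AEs least protected.

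A reader might also infer that deaths after the visit are counted as absent. That is not shown. SAP 15.3.1 draws deaths from the Death and Survival Follow-Up CRFs, SAP 9.5 uses the latter for participants off treatment, and the eCRFs are not part of the documents. The weakness is one of assurance. The current schedule has no survival follow-up visit. Appendix 4 makes fatal progression reportable only within the 8.3.1 period. The SAP's death listing is built from fatal AEs, so it shares the AE cut-off.

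A third tempting step is to say that a material share of participants falls in the 60-day gap because treatment averages about 47 days. That figure (105 − 28 − 30) assumes that the 105 days in Protocol 4.1 include full screening and follow-up. The wording also allows 105 − 28 = 77 days, or 105 days of treatment. Someone stopping at the first scan at 6 weeks (about Day 42) has an earliest visit near Day 42 + 23 = Day 65, past Day 60. Only participants who stop earlier are exposed, and the documents do not say how many.

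Finally, 7 days is the worst case; evenly spread visits give 1.9 days on average. That is fair and limits the size. The 30-day gap also depends on the visit date, not on how early treatment stopped, so the documents do not show that it falls mainly on early stoppers.

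**Conclusion.** The point holds in limited form. Under Protocol 8.3.1, collection may end on Day 23 while the TEAE, on-treatment and 30-day death windows end on Day 30. Up to 7 of 30 days can lack active collection of new AEs, chiefly non-serious ones, and a participant whose only event falls there is counted as event-free. The direction is downward. The size depends on actual visit dates and on which of the conflicting passages sites follow; the incidence and survival figures above rest on assumed rates, a constant hazard and the worst-case visit date.

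Section 8.3.1, the Table 1 note and Section 4.4 must be reconciled. Separately, vital status at 60 days from first dose is not assured for participants whose last dose falls before about Day 23 (visit at +37) to Day 37 (visit at +23). The share affected is unknown. The documents do not establish an undercount of deaths, and they do not support any effect on the 21-day DLT analysis.

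**What to change.** 1. In Table 1 and Protocol 4.1, make the safety follow-up window 30 (+7) days. Alternatively, keep ± 7 and require AE and vital-status ascertainment through at least Day 30, with a brief contact when the visit is earlier.
2. Align Protocol 8.3.1, the Table 1 note and Section 4.4 on one end of AE/SAE collection, and name the contact that delivers any follow-up beyond the visit.
3. In SAP 15.3.1, report the 30-day and 60-day deaths with the number of participants whose vital status is known at that time, alongside the full-set denominator. Known-status participants should not replace the full set: reported deaths always count while uncontacted survivors drop out, which can push the rate up.
4. Reconcile the Survival Follow-Up source in SAP 9.5 and 15.3.1 with the schedule. Simply deleting it could discard death data. Item 1 does not secure the 60-day count; if that count is to be complete, it needs a vital-status check at Day 60 for those who stop early.

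**Cost.** Slightly less scheduling freedom for sites, or one short contact for participants seen early, plus wording changes. No clinic visit is added.
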